3.4.2.3 BMI, Waist Circumference, and Body Weight

The change and percent change from baseline in BMI, Waist Circumference and Body Weight at each analysis visit will be analyzed using a mixed-model repeated-measures (MMRM). The factors in the model will be treatment group (pooled EYP001a and placebo for Part A, each EYP001a group and placebo for Part B), stratification factors – statin use and T2DM status at screening for Part A or statin use and LFC stratification category for Part B, baseline value, visit and the treatment-by-visit interaction. An unstructured covariance matrix will be used (TYPE=UN). The LSMeans for change from baseline at each post-baseline visit will be estimated and compared between the treatment groups.

3.4.2.4 Waist to Hip Ratio and Waist to Height Ratio (Part B Only)

The change and percent change from baseline waist to hip ratio and waist to height ratio at each analysis visit will be analyzed using a mixed-model repeated-measures (MMRM). The factors in the model will be treatment group (each EYP001a group and placebo), stratification factors – statin use and LFC stratification category, baseline value, visit and the treatment-by-visit interaction. An unstructured covariance matrix will be used (TYPE=UN). The LSMeans for change from baseline at each post-baseline visit will be estimated and compared between the treatment groups.

3.4.2.5 Lipoprotein Profiles

Descriptive statistics of each safety laboratory parameter will be presented for baseline values and for values and the change and percent change from baseline at each post-baseline visit. Values outside the normal range will be categorized as H (high, i.e. above the normal range) or L (low, i.e. below the normal range) based on the central laboratory's normal reference range. The number and percentage of patients with values outside the normal range will be summarized by parameter for each post-baseline visit.

The change and percent change from baseline in each of Lipoprotein Profiling parameters (excluding triglycerides) at each analysis visit will be analyzed using a MMRM. The factors in the model will be treatment group (pooled EYP001a and placebo for Part A, each EYP001a group and placebo for Part B), stratification factors – statin use and T2DM status at screening for Part A or statin use and LFC stratification category for Part B, baseline value, visit and the treatment-by-visit interaction. An unstructured covariance matrix will be used (TYPE=UN). The LSMeans for change from baseline at each post-baseline visit will be estimated and compared between the treatment groups.

For analysis of the lipid and metabolic profile, only fasted values of cholesterol, lipoproteins, HDL-C, LDL-C and triglycerides will be included. The listing for these parameters will include the all results and an indicator of the fasting status of the patient at the time the sample was taken.

A sensitivity analysis will also be carried out on the Lipoprotein Profiling to investigate the effect of statin comedication; this analysis will use the same MMRM models as detailed above but with the addition of the interaction for statin use-by-treatment.

For Part A and B, non-parametric analysis will be used for triglycerides. An unstratified Wilcoxon based analysis will be performed and the Hodges-Lehmann estimate along its 95% confidence intervals will also be provided.

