Patients in Part B will be randomized on Day 1 to 1 of 3 parallel treatment groups: 100 mg EYP001a QD, 200 mg EYP001a QD, or placebo QD, with approximately 30 patients in each group. Pruritus-related tolerance issues will be addressed by a 2-step study drug titration strategy for the highest dose treatment group (ie, 200 mg QD): all patients randomized to an active treatment group will start with an initial dose of 100 mg QD for the first 2 weeks of treatment (Days 1 to 14). Patients randomized to the 200 mg QD treatment group will be uptitrated to 200 mg QD starting Day 15 until Day 84, while patients randomized to the 100 mg QD treatment group will maintain a 100 mg QD dose throughout their participation. The study treatment assignment strategy will ensure that blind is maintained.

Randomization will be stratified by statin use (yes, no) and LFC (stratification factor with 3 categories: LFC<16%, 16%≤LFC<22%, and 22%≤LFC) at screening.

Participation in Part B of the study will consist of a Screening Period (up to 12 weeks prior to Day 1), a 12-week Treatment Period, and a Follow-up Visit at Week 14; total study duration is up to 182 days. All eligibility criteria must be confirmed prior to dosing on Day 1.

The 12-week Treatment Period in Part B will include 7 study visits on the following days: Days 1, 14, 28, 42, 56, 70, and 84. Clinical, hematological, chemical, PD, and PK parameters will be

assessed throughout the study. The safety and tolerability assessments will include the monitoring of adverse events; AESIs (ie, elevation of transaminases and all muscle-related adverse events); SAEs; and findings from physical examinations, vital signs, ECGs, and clinical laboratory parameters.

Throughout the study, all TEAEs, clinical assessments, and clinical laboratory parameters will be closely monitored against the criteria for drug-induced liver injury and muscle toxicity as detailed in the Clinical Safety Monitoring Plan ([Appendix E](#)). All adverse events will be assessed and reported using the National Cancer Institute CTCAE Version 5.0 grading system. Additional safety measurements will be performed at the discretion of the Investigator (or delegate). At screening and on Days 1, 14, 28, 56, and 84; and at the End of Study (EOS) and Early Termination (ET) Visits, plasma from blood samples will be stored for protocol-related safety testing or exploratory analyses.

Data Safety Monitoring Committee and Interim Analyses

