5.6.2 Restricted Medications and/or Procedures

Patients receiving statin therapy (rosuvastatin, atorvastatin, simvastatin, pravastatin, fluvastatin, or lovastatin are the only allowable statins) need to be on stable therapy for at least 90 days prior to the first administration of study drug. If LDL-C increases >10 mg/dL at Week 2, the statin dose may be increased and titrated up at the following visit if the LDL-C remains 5% above the baseline value.

For patients without statin therapy at baseline, if LDL-C increases $\geq 25\%$ from Day 1 to Day 14, rosuvastatin 20 mg QD will be introduced and titrated up to 40 mg QD at the following visit if LDL-C remains 5% above the baseline value.

Patients receiving other lipid-lowering treatments need to be on stable therapy for at least 90 days prior to the first study drug administration and must agree to remain on a stable regimen for their entire participation in the study. Patients with T2DM should be on a stable dose of antidiabetic medication for at least 90 days prior to screening and must agree to remain on a stable regimen for their entire participation in the study.

Close monitoring is required for comedication agents that are substrates for CYP2C8 or CYP2C9.

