3.1.4 Analysis Visits

Refer to SAP V1.0 for Part A analysis visits.

Part B

For LFC, cT1, LSM and CAP, analysis visits will be assigned according to the labelled visit. I.e. "Baseline" analysis visit will be sourced from the "Screening" visit, and "Week 12/ET" analysis visit will be sourced from the "Week 12" or "ET" visit. Note that the ET assessment will be performed only for patients on study drug for ≥4 weeks.

For all other efficacy assessments with regular scheduled visits, analysis visits will be assigned according to the labelled visit. In addition to maximize the data available for assessments with regular scheduled visits, where possible, results from ET and unscheduled visits will be allocated to a post-baseline scheduled visit according to the following rules and visit windows

described in the table below (defined as the halfway point between the target visit days). If a valid value exists for the scheduled visit to which the ET/unscheduled visit has been allocated then the value from the scheduled visit will be used in the analysis, otherwise the values from the ET/unscheduled visits will be used in the analysis for the particular scheduled visit. If there is more than one assessment within a visit window, then the analysis visit will be assigned by the following priorities:

1. Use the assessment from the visit with the matching visit label.
2. Use the visit closest to the target visit day; in the case of ties, use the earlier visit.

Analysis Visit and Target Analysis Day	Visit Windows (Analysis Days)		
	Group I	Group II	Group III
Baseline	See Section 3.1.3		
Day 14 (Week 2)	2 – 21	2 – 21	
Day 28 (Week 4)	22 – 35	22 – 42	2 – 42
Day 42 (Week 6)	36 – 49		
Day 56 (Week 8)	50 – 61	43 – 70	43 – 77
Day 70 (Week 10)	62 – 77		
Day 84 (Week 12)	78 – 91	71 – 91	
Day 98 (Week 14) EOS FUP	92+	92+	92+
Group I: ALT, AST, AST/ALT Ratio, ALP, Total Bilirubin, Gamma-glutamyltransferase (GGT)			
Group II: hs-CRP, CK, BMI, Waist Circumference, Body Weight, Waist to Height Ratio, Waist to Hip Ratio, and lipids and metabolic profile			
Group III: HbA1c and all other biomarkers of liver fibrosis and inflammation			

Note that parameters that are considered both efficacy and safety (ALT, AST, CK) will use analysis visit windowing for both the efficacy and safety summaries and analyses for Part A and Part B.

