A similar summary will be provided for the mITT Population and Per-Protocol Population if the size of the population is different (>10%) from the size of the ITT Population for any treatment group.

Demographic characteristics include age, gender, ethnicity and race.

Baseline characteristics include:

- Stratification variables – statin use and T2DM status at screening (Part A), statin use and LFC category at screening (Part B);
- LFC as assessed from MRI-PDFF;
- cT1;
- LSM and CAP as assessed by FibroScan;
- Anthropometric parameters – height, weight, BMI and waist circumference, waist to hip ratio (Part B), waist to height ratio (Part B)
- Vital Signs – systolic blood pressure (SBP), diastolic blood pressure (DBP), heart rate (HR), Respiratory Rate and Temperature
- Alcohol use (Alcohol Use Disorders Identification Test-Concise [AUDIT-C] Total Score);
- Biomarkers of liver fibrosis and inflammation;
- Liver Function Tests – ALP, Total Bilirubin, GGT, International normalized ratio (INR) and Albumin.

Stratification variables will be sourced from the value used for randomization stratification, even if it is later found to be incorrect based on the patient data. Mis-stratification will be flagged in the listings.

3.3.5 *Medical History*

Medical history will be coded using the Medical Dictionary for Regulatory Activities (MedDRA) version 22. The number and percentage of patients with medical history will be summarized by

preferred term within system organ class and treatment group for the Randomized Population and presented by descending overall frequency of system organ class, and within system organ class by descending incidence of preferred term

All reported medical history will be listed.

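### After Week 2 the Part B LDL-C contrasts estimate EYP001a plus the protocol's LDL-triggered statin changes; the SAP does not say so and plans no estimate without them

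*SAP*

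**What the plan says.** **Statin rule (Protocol 5.6.2).** For patients without a baseline statin, the trigger is a Day 14 LDL-C at least 25% above the Day 1 value. In that case "rosuvastatin 20 mg QD will be introduced and titrated up to 40 mg QD at the following visit", the titration applying only where LDL-C is still 5% above baseline. This start is mandatory. For baseline users the rule is permissive: "If LDL-C increases >10 mg/dL at Week 2, the statin dose may be increased and titrated up at the following visit".

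**Dosing (Protocol 3.1, Part B).** Both active arms take 100 mg QD on Days 1 to 14. The higher-dose arm "will be uptitrated to 200 mg QD starting Day 15 until Day 84".

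**Lipid visits (Protocol Table 8).** Post-baseline lipids are drawn on Days 14, 28, 56, 84 and 98 and at early termination. Days 42 and 70 have liver tests only. Treatment ends on Day 84.

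**Analysis (SAP 3.4.2.5).** Change and percent change in each lipoprotein parameter except triglycerides "at each analysis visit will be analyzed using a MMRM". The Part B model has treatment, the statin and LFC stratification factors, baseline, visit and treatment-by-visit. "The LSMeans for change from baseline at each post-baseline visit will be estimated and compared between the treatment groups". The only restriction on the data is fasting status. One sensitivity analysis fits the same model "with the addition of the interaction for statin use-by-treatment".

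**Definitions.** SAP 3.4.2.5 lists statin use among the stratification factors, and SAP 3.3.4 adds: "Stratification variables will be sourced from the value used for randomization stratification". In SAP 3.1.4, lipids are in the visit-window group that includes "Waist to Height Ratio, Waist to Hip Ratio, and lipids and metabolic profile". Its Week 2 window is Days 2 to 21, and the scheduled visit takes priority. SAP 3.3.6 tabulates prior and concomitant statins by type, but does not ask for on-study starts or dose increases.

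**The concern.** The variable that triggers the statin change is the outcome being analysed. If EYP001a raises LDL-C, more active than placebo patients cross the threshold and more receive added statin, so later LDL-C is lowered more in the active arms. If EYP001a lowers LDL-C, the imbalance runs the other way. In both directions the later contrasts move toward zero as estimates of what the drug itself does.

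Effects on the lipid profile are a secondary objective (Protocol 2.2), and LDL-C is among the six efficacy variables in the first-lock analysis (SAP 4.2). Protocol 1.2.3 treats lipid change as an apparent class effect of unknown long-term risk, to be weighed against benefit. When LDL-C rises, an unlabelled and attenuated contrast errs on the reassuring side.

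**Working it through.** **1. Timeline for the 200 mg arm.**

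| Lipid visit | Dose | Relative to the Week 2 trigger |
|---|---|---|
| Day 14 | 100 mg | before |
| Days 28, 56, 84 | 200 mg | after |
| Day 98 | off drug | after |

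None of the three on-200-mg visits precedes the trigger. Week 2 is essentially free of triggered changes, but it is a 100 mg contrast in both active arms, apart from any early-termination or unscheduled value from Days 15 to 21.

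**2. Inputs.** The documents give no LDL-C effect, SD or trigger rate, so there is no plan figure to reproduce. All of the following are assumed: percent change in LDL-C is normal with SD 15 or 20; correlation between visits 0.6; half of patients are non-users; added statin lowers LDL-C by a fraction s = 0.2 or 0.5; no increases in users; both active arms share the same Day 14 mean.

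**3. Formula.** A triggered non-user's later level is multiplied by (1 - s). With mean Day 14 change m and mean later change L in an arm:

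- a = (25 - m)/SD, and trigger probability p = 1 - Φ(a)
- mean later level in triggered patients M = 100 + L + 0.6 × SD × φ(a)/p
- loss in the contrast = 0.5 × s × (p×M on active - p×M on placebo)

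With no drug effect the two products are equal and the loss is zero.

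**4. True Week 8 difference +10 (100 mg) and +20 (200 mg), Day 14 effect +10.**

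- SD 15, s = 0.2. Placebo: p = 0.0478, M = 118.7. Active: p = 0.1587, M = 123.7 (100 mg) or 133.7 (200 mg). Losses: 0.1 × (19.63 - 5.67) = 1.40 and 0.1 × (21.22 - 5.67) = 1.55. Observed: about 8.6 and 18.4.
- SD 20, s = 0.5. Placebo: p = 0.1056, M = 120.7. Active: p = 0.2266, M = 125.9 or 135.9. Losses: 0.25 × (28.53 - 12.75) = 3.95 and 0.25 × (30.79 - 12.75) = 4.51. Observed: about 6.1 and 15.5.

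**5. Simulated MMRM, same inputs, Week 8.** It agrees with the formula to about 0.1 point.

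| True 100 / 200 mg | Estimated 100 mg | Estimated 200 mg |
|---|---|---|
| +7.5 / +15 | 4.7 to 6.6 | 11.8 to 14.0 |
| +10 / +20 | 6.0 to 8.6 | 15.6 to 18.5 |
| +15 / +20 | 8.3 to 12.4 | 13.0 to 17.2 |
| +10 / +10 | 6.0 to 8.6 | 5.9 to 8.6 |
| -10 / -15 | -8.0 to -9.5 | -13.0 to -14.6 |

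In the four rows with a rise, the loss is 0.9 to 7.1 points: 12-45% at 100 mg and 7-41% at 200 mg.

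**6. Scale.** The unadjusted standard error at 30 per arm is SD × √(2/30) = 3.9 (SD 15) to 5.2 (SD 20). Only +15 / +20 with 50% statin lowering clearly loses more than one standard error.

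**7. The planned interaction model.** In the +10 / +20 case its Week 8 estimate for baseline users is 8.0-9.5 / 17.9-19.6. If half of the users who rise more than 10 mg/dL are increased (assumed baseline LDL-C 100 mg/dL, extra 6% lowering), it falls to 7.4-9.0 / 17.1-18.8. Recovery is incomplete because the interaction is not by visit. The non-user stratum gives no clean estimate, since that is where the start is mandatory and a started patient stays coded as a non-user.

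**The case against.** The planned contrast is a legitimate effect of assignment to EYP001a with statin added as needed. The rule applies to all arms, and the contrast has no bias when the drug has no effect. This stands: a reader might infer that the LDL-C analysis is invalid, and the documents do not support that. What is missing is the label and a companion estimate.

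The stakes are modest. Protocol 7.1.2 lists no lipid variable among its secondary efficacy variables, SAP 2.1.2 names LDL cholesterol as an input to an insulin resistance index, and the first-lock list in SAP 4.2 is an early subset rather than an endpoint hierarchy. This also stands, and it limits the point to a cheap improvement.

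The plan already investigates statin comedication. It does, and in baseline users the interaction model recovers most of the assumed effect. It does not isolate the drug effect in non-users, and it leaves users' own dose increases in the data.

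A reader might also infer that Part B should have a statin-free visit, or that the 200 mg effect is wholly masked. Neither follows. Statin users are enrolled by design, so the issue is only LDL-triggered changes. The mandatory start depends solely on the Day 1 to Day 14 rise at 100 mg, so a rise that first appears at 200 mg starts no rosuvastatin. In the simulated cases with an LDL-C rise, 69-88% of active non-users never start.

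**Conclusion.** The mechanism follows directly from the documents. After Week 2, the Part B LDL-C contrasts combine EYP001a with LDL-triggered statin changes; the SAP does not say so; and no lipid visit on 200 mg is free of such changes. As an estimate of the drug's own effect the contrast is attenuated if, and only if, EYP001a changes LDL-C.

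The size cannot be derived from the documents. The illustrated losses rest wholly on the assumed effects, SD, correlation, share of users and statin potency, and most are within one standard error. The loss is a smaller share at 200 mg only where a larger 200 mg effect is assumed. Confidence is high in the mechanism and low in any particular size.

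The primary LFC analysis is not affected, and nothing here calls for a change to the clinical statin rule. The point is worth acting on because it bears on a stated objective and costs little.

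**What to change.** In SAP 3.4.2.5 and 3.3.6:

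1. Keep the as-observed MMRM. Label its contrasts after Week 2 as EYP001a plus statin as needed.
2. Add one supplementary LDL-C MMRM, same model, with LDL-C set to missing from the first on-study statin start or dose increase. Confine it to LDL-C, because for other lipids the trigger (Day 14 LDL-C) is not in the model.
3. In the SAP 3.3.6 statin table, show on-study starts and dose increases by arm. Protocol 5.6.3 already captures these changes in the eCRF.

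**Cost.** Some SAP wording, one extra model run and a few table rows. No new data are needed.

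**Downsides to state with the supplementary model.**

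- *Precision.* In simulated trials of 30 per arm (statin effect 35%), Week 8 standard errors are 0-4% larger than with complete statin-free data if only non-users start. They are 5-11% larger if half of the users above 10 mg/dL are also increased.
- *Missing at random.* This is reasonable for non-users, whose trigger is in the model, although all of their later values are then extrapolated. It is weaker for discretionary increases in users. In the cases with an LDL-C rise, the estimate is within 0.2 point if those increases are random given Day 14, and 0.3-0.9 low if they are three times as likely in users whose later LDL-C runs higher. The as-observed contrast in the user-increase runs is 1.2-7.8 low.
- *Uniform response.* If Day 14 responders at 100 mg respond proportionally more at 200 mg (assumed response SD 5-15), the 200 mg estimate is 0.2-1.8 points low, though still closer to the truth than the as-observed contrast.

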3.5 Pharmacokinetic Assessment

Further details concerning the display and analysis of the PK data will be included in a separate PK Analysis Plan and is out of the scope of this SAP.

3.6 Pharmacodynamic Assessment

Further details concerning the display and analysis of the PD data will be included in a separate PD Analysis Plan and is out of the scope of this SAP.

3.7 Safety Assessment

The safety data for this study include AEs, pruritus assessments, safety laboratory assessments, vital signs and anthropometrics, ECGs and physical examinations. The safety data will be summarized based on the Safety Population and presented by treatment group. Missing values will not be imputed. All reported safety data will be listed for the Randomized Population.

3.7.1 Adverse Events (AEs)

An AE is defined as any untoward medical occurrence in a clinical investigation patient administered a pharmaceutical product, which does not necessarily have a causal relationship with this treatment. An AE can therefore be any unfavorable and/or unintended sign (including an abnormal laboratory finding), symptom, or disease temporally associated with the use of an investigational medicinal product, whether or not related to the investigational medicinal product.

For analysis, a treatment emergent AE (TEAE) is defined as a new or worsening AE after the first dose of study drug. Programmatically, this will be identified as any AE with a start date on or after the date of first dose. If part of the date for the onset/end of an AE is missing, but the existing parts allow determination of timing of AE onset relative to the first dose of study drug, then the AE will be classified as treatment-emergent or not per review of the existing parts of the date. If timing of the AE onset/end relative to the first dose of study drug cannot be determined, then the AE will be assumed to be treatment-emergent.

A summary overview of all AEs will be provided, which presents the number and percentage of patients in each treatment group from the Safety Population, including number of events, satisfying each of the following categories:

- Any AE
- Any TEAE
- Maximum severity of TEAEs
- Study drug-related TEAEs
- Maximum severity of study drug-related TEAEs
- TEAEs of special interest:
 - Part A: pruritus, Drug Induced Liver Injury (DILI) and muscle-related

➤ Part B: elevation of transaminases and muscle-related

- All serious AEs (SAEs)
- All serious TEAEs (TESAEs)
- All study drug-related TESAEs
- TEAEs leading to early discontinuation
- TEAEs leading to temporary discontinuation of study drug
- TEAEs leading to dose reduction

AEs will be coded using MedDRA v22. The number and percentage of patients with AEs, including the number of AEs, will be summarized by their MedDRA preferred term within system organ class and treatment group. For patient count summaries, multiple AE events with the same MedDRA coded terms (preferred term and system organ class) from the same patients will only be counted once. Similar summaries will be presented for study drug-related TEAEs and TESAEs.

The number and percentage of patients with TEAEs will be summarized by reported maximum severity within each MedDRA preferred term within system organ class and by treatment group.

A further summary table for TEAEs by preferred term and system organ class will be provided for patients in the Safety Population who were taking a statin; a separate summary table will be provided for patients in the Safety Population who were not taking a statin. Patients who were and were not taking a statin will be identified from the appropriate stratification variable.

Detailed listings will be provided for all AEs. Separate listings will also be provided for AEs of Special Interest, SAEs, TEAEs leading to early discontinuation, TEAEs leading to temporary discontinuation of study drug and TEAEs leading to dose reduction.

For both Part A and Part B, an additional summary of derived pruritus TEAEs will be provided for the following categories:

- Grade 1 (mild or localized), defined as (severity grade 1 and (flagged as pruritus AESI on the eCRF or preferred term="Pruritus generalised")) or preferred term = "Pruritus"
- Grade 2 (widespread and intermittent), defined as severity grade 2 and preferred term = "Pruritus generalised"
- Grade 3 (widespread and constant), defined as severity grade 3 and preferred term = "Pruritus generalised"

3.7.2 *Pruritus Assessments*

Part A

The pruritus visual analog scale (VAS) and 5-D (degree, duration, direction, disability and distribution) itch scale will be assessed at Days 1, 7, 14, 21, 28, 56, 84 and 98 and also at the ET Visit.

Descriptive statistics for the pruritus VAS and 5-D itch scale will be presented for baseline values and for values and the change from baseline at each post-baseline visit.

Part B

In Part B, pruritus will be reported as any other AE. If a patient reports pruritus, the visual analog scale and the 5-D questionnaire (degree, duration, direction, disability, and distribution) itch scale will be administered. Results will be listed.

